will estimate the statistical significance of the entire family (“familywise error rate”) using stepdown resampling methods in Westfall and Young (1993) and Westfall, Tobias and Wolfinger (2011). Pre-registered clusters of measures are identified with grey bars in appendix tables.

Data release. We are releasing data and documentation from the study to the research community through the Inter-university Consortium for Political and Social Research approximately 18 months following the end of each data collection wave to enable independent researchers to pursue replication, mediation, moderation as well as other related analytic questions.

Additional Details for Age 6 and 8 Resting EEG Hypotheses and Analyses

Consistent with our approach at age 4, we are updating our analysis plan for the ages 6 and 8 collection with primary and secondary hypotheses that have been informed by results from our age-1 resting EEG treatment impacts (Troller-Renfree et al., 2022) and, in the case of age 6, our ongoing but as yet unpublished analyses of the age-4 resting EEG data. As with other outcomes at ages 6 and 8, we now provide directional hypotheses for all our pre-registered primary and secondary hypotheses and will assess them using one-tailed tests (see discussion below).

Our analysis plan includes preregistration of an index of mid- to high-frequency power (described below; primary hypothesis) as well as a more traditional neuroscientific investigation of power within bands (described below; secondary hypotheses). Please see the history of preregistrations, including analysis plans, for more detail.

Ages 6 and 8 primary hypothesis and analyses: Because of limitations in power expected with multiple testing adjustments, we are preregistering a single composite index of mid-to-high-frequency whole-brain power summed across alpha, beta, and gamma bands (defined as between 7 and 45 Hz). This frequency composite index sums absolute power across all single-Hz interval in the Alpha, Beta, and Gamma bands.

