A second set of secondary analyses are based on a different estimation approach. Consistent with another RCT examining brain activity (Debnath et al., 2020; Marshall et al., 2004; Vanderwert et al., 2010, 2016), we will analyze band-specific effects using mixed-effects models, with group as the between-subjects factor and region as within-subjects factor, to examine ITT impacts on each band of relative power in the eyes-closed condition. Bands will be defined as follows: Theta 3-6 Hz, Alpha 7-12 Hz, Beta 13-20 Hz, Gamma 21-45 Hz. Again, covariates will include all preregistered covariates as well as the number of artifact-free epochs contributed by each participant. Power values above the 99th percentile of their respective power band distribution in absolute power will be truncated from above at the 99th percentile. Our secondary hypotheses for each band are as follows: Theta (high-cash<low-cash), Alpha (high-cash>low-cash), Beta (high-cash>low-cash), and Gamma (high-cash>low-cash). One-tailed t-tests will be used given directional hypotheses. No further multiple-testing adjustments beyond the use of multi-level models will be used (Gelman et al., 2012).

The mixed effects models will also enable us to rank the four power bands by the (absolute) size of their impacts. Although we are not preregistering hypotheses regarding these rankings, we can record our expectations about them. Based on past results from this project (Ages 1 and 4), a review of the relevant literature, and the expertise of our neuroscience team, we expect that the cash gift impact will be largest in the Alpha band at both ages 6 and 8. Following Alpha, associations between SES and Theta are the most reported in the literature and, as such, we expect that the impact of the cash gift will second largest in the Theta band, although we have seen no indication of this difference at Ages 1 and 4. Finally, some group differences in Beta and Gamma were detected at Age 1, but preliminary analyses suggest these are not detectable at age 4. Continuous, correlational relations between SES and Beta and Gamma are less consistent in the broader literature (perhaps as these bands are easily influenced by artifacts, as we saw some evidence of at Age 4), leading us to expect that impact of the cash gift will be smallest for these bands at Ages 6 and 8. In supplemental, exploratory analyses, we will report the same analyses for absolute power and in the eyes-open condition.

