Age-1 Resting Brain Function	Tomalski et al., 2013; Otero et al., 2013; Marshall et al., 2004	n/a		1	Measured by low-density mobile electroencephalography at Age 1: we preregistered group differences in theta, alpha, gamma power.
Age-4 Resting Brain Function	Tomalski et al., 2013; Otero et al., 2013; Marshall et al., 2004; Troller-Renfree et al. 2022	n/a	4	4	Measured by high-density in-lab electroencephalography (EEG) Age-4 Primary: Because of limitations in power expected with multiple testing adjustments, we are preregistering a single composite of mid-to-high-frequency whole-brain power summing across alpha, beta, and gamma bands, from 7 to 45 Hz. Age-4 secondary: We hypothesize greater frontal gamma power in the high-cash gift group, and plan to analyze a full model of regions nested within bands, with the plan to report all exploratory outcomes. See attached analysis plan. Note: The original preregistration of EEG data collected when children were 12 months old included hypotheses across multiple frequency bands. Please see the history of preregistrations, including analysis plans.
Age-6 and Age-8 Resting Brain Function	Brito et al., 2020; Brito et al., 2022; Cantiani et al., 2019; Debnath et al., 2020; Gelman et al., 2012; Maguire et al., 2019; Marshall et al., 2004; Rockers et al., 2023, Troller-Renfree et al., 2022; Vanderwert et al., 2010; Vanderwert et al., 2016		6, 8		Measured by high-density in-lab electroencephalography (EEG). Ages 6 and 8 Primary hypothesis: Because of limitations in power expected with multiple testing adjustments, we are preregistering a single composite index of mid-to-high-frequency whole-brain power summed across alpha, beta, and gamma bands (defined as between 7 and 45 Hz). This frequency composite index sums absolute power across all single-Hz interval in the Alpha, Beta, and Gamma bands. We hypothesize that, in the eyes-closed condition, the high-cash gift group will show more power in this composite relative to the low-cash gift group. One-tailed t-tests will be used to test this directional hypothesis. See the Statistical Analysis Plan for additional details.

Domains (in gray) and sub-domains	Measure source	Psychometrics	Age preregistered Primary Outcome	Age preregistered Secondary Outcome	Measures and notes (All measures between grey lines measured in the same wave will be subject to multiple testing adjustments)

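### The four one-tailed EEG band tests at ages 6 and 8 rely on multi-level models for multiplicity control, but the stated model specifies no pooling across bands and the exemption is not reconciled with the SAP's own adjustment rule

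*SAP*

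**What the plan says.** The Phase 2 section on resting EEG at ages 6 and 8 sets out a second group of secondary analyses. The structure of the mixed models is given as "with group as the between-subjects factor and region as within-subjects factor". Each frequency band, measured as relative power with eyes closed, gets its own intent-to-treat estimate. There is one hypothesis per band: lower theta in the high-cash group, and higher alpha, beta and gamma. On the tests: "One-tailed t-tests will be used given directional hypotheses". On multiplicity: "No further multiple-testing adjustments beyond the use of multi-level models will be used", with one methods paper cited. The ages 6 and 8 secondary row of Appendix Table 9 repeats this sentence.

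Two other places give a general rule. The Phase 2 section on multiple comparisons says that, for related measures that cannot be combined into one index, the team "will estimate the statistical significance of the entire family" by Westfall-Young step-down resampling. The notes column of Table 9 is headed: "All measures between grey lines measured in the same wave will be subject to multiple testing adjustments". The band hypotheses sit under that heading, in the Resting Brain Function domain.

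The primary EEG outcome is a single composite over 7-45 Hz, exempted from adjustment on a separate ground: it is one index score.

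**The concern.** A multilevel model moderates multiple comparisons only if the effects being compared are themselves partially pooled, that is, drawn toward one another. Here those effects are the four group differences, one per band. The only within-child factor named is region. Modelling region within child deals with correlation among scalp regions for a given band. It does not pull the theta, alpha, beta and gamma group effects together. On the stated structure each band test keeps its full error rate, and the sentence offers a safeguard that the model does not supply.

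The SAP also gives the analyst two incompatible instructions for the same pre-registered tests. One says to adjust within domain and wave; the other says not to. They can give different significance calls.

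The plan itself treats the bands as a multiplicity problem. The Phase 1 EEG section explains that power was inadequate for testing several bands, and Phase 2 adopts the composite because of the power expected to be lost to adjustment. The reason that exempts the composite, a single score, cannot cover four separate band tests.

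**Working it through.** **Inputs.** Four one-tailed tests per age (Phase 2 EEG section). EEG sample of 700 split 40/60, so 280 and 420 (Phase 2 power section). EEG sample achieved at age 4: 634 (Phase 2 attrition section). The level per test is an assumption: the EEG section states none, and .05 one-tailed is taken from the power section. The correlation between bands is also an assumption: the Phase 1 EEG section calls it high but gives no figure.

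**Reproducing the plan's own figure.** Standard error in sd units: sqrt(1/280 + 1/420) = 0.0772.
- One-tailed detectable effect at 80% power: (1.645 + 0.842) × 0.0772 = 0.192, against .19 stated.
- Two-tailed: (1.960 + 0.842) × 0.0772 = 0.216, against .22 stated.

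Both reproduce. They apply to a single unadjusted test.

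**Does the stated model shrink the band effects?** A mixed model with region within child was fitted to simulated balanced data, one band at a time. In all four bands the group estimate and its standard error equalled the raw difference in region means (for example 0.08601, SE 0.06763, both ways). There was no shrinkage.

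**Family-wise error with four unadjusted tests at .05 one-tailed, per age.** Correlations are between test statistics signed in the hypothesised direction.

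| Assumption | Chance of at least one false positive |
|---|---|
| Independent: 1 − .95^4 | 18.5% |
| Relative powers sum to 1, exchangeable (correlation −1/3, theta sign reversed) | 17.6% |
| Relative powers sum to 1, three other simulated set-ups | 14.9% to 17.3% |
| Equal correlation .5 | 14.4% |
| Equal correlation .8 | 10.6% |
| Equal correlation .9 | 8.8% |

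**Cost of adjusting (single-step, N=700).** Detectable effect = (critical value + 0.842) × 0.0772. Power at .19 sd = Φ(.19/0.0772 − critical value).

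| Case | Critical value | Per-test level | Detectable effect | Power at .19 sd |
|---|---|---|---|---|
| Unadjusted | 1.645 | .0500 | 0.192 | 79% |
| Max-T, correlation .9 | 1.93 | .0268 | 0.214 | 70% |
| Max-T, correlation .5 | 2.16 | .0154 | 0.232 | 62% |
| Max-T, independent | 2.233 | .0128 | 0.237 | 59% |
| Bonferroni | 2.241 | .0125 | 0.238 | 59% |

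At the age-4 sample of 634, the Bonferroni detectable effect is 0.250 sd.

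**The case against.** **The absence of pooling is inferred.** The SAP does not say that the bands are fitted separately. It uses the word separate where it means it, for the age-4 band ANOVAs and for eyes-open against eyes-closed, and not here. It also says the models will allow the bands to be ranked, so a joint model is conceivable. This stands as a limit on the claim: what the documents show is that pooling across bands is not specified. But ranking needs only four estimates, the listed changes from age 4 mention no joint model, and fixed group-by-band terms would not pool either. A random group-by-band effect would; an approximate version of it, with independent tests, gave about 9%, still above 5%.

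**It is a declared exception.** The sentence is specific, cited and stated twice, and the section on multiple comparisons says several approaches will be drawn on. It can fairly be read as a deliberate carve-out. Even so, neither the table heading nor the general rule mentions it, and its stated basis does not fit the stated model.

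**Stronger readings that a reader might infer, and that the documents do not support.**
- That the eyes-open composite is exempt too, giving 1 − .95^5 = 22.6%. The exemption closes the paragraph on the band models, and nothing exempts the eyes-open composite, so the table heading would cover it. Independence of five measures from the same children is also implausible.
- That a chance band finding is likely. The range is about 9-18%: well above 5%, but not likely.
- That this domain is treated more leniently than all others. Several domains hold one measure per wave, such as math or BMI, where no adjustment arises.
- That the main EEG result is compromised. The primary composite is a single test.

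**Conclusion.** The concern holds in this form: as written, the model gives the four band tests no multiplicity protection across bands, and the exemption is unreconciled with the SAP's general rule. Family-wise error per age is about 9-18% against 5% nominal. The size depends on the assumed .05 one-tailed level, on the band correlations, and on how relative power is formed, since the SAP does not define its denominator. Some inflation remains at any correlation short of perfect. The conclusion about pooling rests on the factors that the SAP names and would change if a pooled cross-band model were written out.

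Because these are secondary hypotheses and the exception is openly stated, this should be fixed before the age-6 and age-8 band results are analysed, but it does not threaten the trial's primary EEG inference.

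**What to change.** Replace the no-adjustment sentence in the Phase 2 EEG section and in the matching Table 9 row with one of these:

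1. One-sided Westfall-Young step-down across the four band tests within each age, resampling whole children so that the correlation among bands and regions is kept. This is the plan's own method.
2. One joint model across bands, with group-by-band effects as partially pooled random effects signed in the hypothesised direction, written out in full and named as an exception in the Table 9 heading. Its error rate should be reported, since pooling alone need not bring it to 5%.

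In either case, state that the eyes-open composite stays under the Table 9 rule and that the primary composite remains a single test.

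The cost is SAP wording plus one resampling run or one model specification, and some power. Under single-step adjustment at N=700 the detectable effect rises from .19 to about .21-.24 sd, and power at .19 sd falls from 79% to about 59-70%, depending on correlation. Step-down recovers some of this after the first rejection.

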A few changes in our EEG analysis plans between age 4 and ages 6 and 8 are worth noting. First, as with other study outcomes, we now provide directional hypotheses for all analyses. As such, we now also propose the use of one-tail analyses to test these hypotheses. This switch to one-tailed tests was motivated by two factors. First, one-tailed tests provide more statistical power for testing our hypotheses. Second, although we had directional hypotheses in the past, these were not always clearly preregistered and, as such, two-tailed tests were used. However, since our initial preregistration, more evidence has emerged linking SES to EEG (Brito et al., 2020, 2022; Cantiani et al., 2019; Maguire & Schneider, 2019; Rockers et al., 2023) as well as our own analyses (Troller-Renfree et al., 2022), which supports our making directional hypotheses for all bands. However, we are still unsure of which brain regions are likely to drive

Analysis Plan for Phase 2

these whole-brain effects as the literature is mixed with significant findings inconsistently observed in almost every region of the brain. As such, we make no region-specific hypotheses.

Additional Details for Age 6 and Age 8 Epigenetic Processing and Analysis

We are preprocessing age 4 genome-wide DNA-methylation on a newly released array (EPIC v2) - see OSF link https://osf.io/ahv2p/?view_only= and will then upload a more detailed age-6 and age-8 DNA-methylation preprocessing pipeline on OSF, which will probably deviate from age 4 given new bioinformatic tools and lessons learned. We will re-preprocess age-4, age-6 and age-8 DNA-methylation together to minimize technical artifacts. We will exclude DNA-methylation sites and samples failing technical criteria (e.g., low detection p threshold, sex mismatch) based on methylation-wide data *before* these preregistered methylation profile scores are computed. We will follow preregistered intent-to-treat analyses described in this document and add the following variables as covariates to DNA-methylation analyses: cell composition, technical DNAm factor (plate), child's age in months at the time of age-6 and age-8 data collection.

We hypothesize the following with regard to *child epigenetic outcomes*:

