- 1) We hypothesize slower pace of aging, as measured by DunedinPACE, in the high-cash gift group, relative to the low-cash gift group. Methylation pace of aging was developed from DNA-methylation analysis of Pace of Aging in the Dunedin Study birth cohort (Belsky et al., 2022). Pace of Aging is a composite phenotype derived from analysis of longitudinal change in 18 biomarkers of organ-system integrity (Belsky et al., 2015). Increments of methylation pace of aging correspond to “years” of physiological change occurring per 12-months of chronological time. We will also report GrimAge Acceleration, which we consider an exploratory analysis. GrimAge represents a DNA-methylation metric designed to predict morbidity and mortality (Lu et al 2019). Briefly, the initial phase entailed the computation of models incorporating physiological indicators, age, sex, and smoking history, with the objective of optimizing mortality prediction within the Framingham Heart Study Offspring cohort (Lu et al., 2019). GrimAge will be based on principal components of DNA-methylation to bolster reliability (Higgins-Chen et al., 2022) and residualized for chronological age derived from sample receipt age to reflect accelerated biological age.
- 2) We hypothesize higher Epigenetic-g in the high-cash group relative to the low-cash gift group. Salivary DNA-methylation profiles of cognitive functioning, i.e., “Epigenetic-g”, can be computed on the basis of weights from a blood-based epigenome wide association study of general cognitive functions (g) in adults (McCartney et al., 2022). General cognitive ability was derived from the first unrotated principal component of logical memory, verbal fluency and digit symbol tests, and vocabulary. Epigenetic-g is

Analysis Plan for Phase 2

conceptually distinct from biological aging. If a higher quality measure of epigenetic profile of cognitive functioning becomes available at the time of analysis, we will substitute that instead.

We hypothesize the following with regard to *maternal epigenetic outcomes*:

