- 1) We hypothesize slower pace of aging, as measured by DunedinPACE (Belsky et al., 2022), in the high-cash gift group, relative to the low-cash gift group. We will also report GrimAge Acceleration (Lu et al 2019; described above) and PhenoAge Acceleration as exploratory analyses. PhenoAge is conceptualized on the foundation of physiological markers and chronological age, which are subsequently employed to model a novel sample derived from DNA methylation, culminating in the establishment of a definitive DNA methylation clock (Levine et al., 2018). This metric exemplifies the age, measured in years, at which the average mortality risk in the NHANES III cohort aligns with the mortality risk as forecasted by the PhenoAge algorithm. PhenoAge will be based on principal components of DNA-methylation to bolster reliability (Higgins-Chen et al., 2022) and residualized for chronological age derived from sample receipt age to reflect accelerated biological age.

Changes to Control Variables Following the Posting of the Phase II Analysis Plan (finalized on July 3, 2025)

As with Age 4 analyses, for our Age 6 and 8 preregistered analyses, we have added controls for child age at the time of the data collection to adjust for age-related developmental differences that may affect both preregistered child and maternal outcomes. In the case of all preregistered outcomes gathered in lab assessments or maternal interviews, we will also control for an indicator for the interviewer/assessor for the specified outcome. In the case of non-survey and non-assessment measures (e.g. tract-level neighborhood poverty rate, school record test scores) we will adjust only for child age at the time of the interview.

These measures were not initially preregistered for analyses of child outcomes (Receptive One-Word Picture Vocabulary Test, Minnesota Executive Function Scale, Child Behavior Checklist, Resting Brain Activity, Matrices, Reading House, and Developmental Condition Diagnosis, age/sex adjusted BMI percentile and maternal report of child health) and maternal outcomes (depression, anxiety, and Body Mass Index (BMI)). Child age controls for age-related developmental differences that may affect both preregistered child and maternal outcomes, while the indicator for the interviewer/assessor has been added to account for any idiosyncratic assessor component to variation in preregistered child and maternal measures based on lab or survey assessments.

Analysis Plan for Phase 2

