Methylation pace of aging	Belsky et al., 2015; Belsky et al., 2020; Belsky et al., 2022; Higgins-Chen et al., 2022; Levine et al., 2018, Lu et al., 2019	n/a		4	Methylation pace of aging was developed from DNA-methylation analysis of Pace of Aging in the Dunedin Study birth cohort. Pace of Aging is a composite phenotype derived from analysis of longitudinal change in 18 biomarkers of organ-system integrity. In contrast, so-called epigenetic clocks are trained on chronological age. Increments of methylation pace of aging correspond to “years” of physiological change occurring per 12-months of chronological time. The second iteration (DunedinPACE) takes into account an additional measurement occasion (collected 20 years after inclusion) and only includes the most reliable DNA methylation probes, i.e. probes with little variation between technical replicates. If a higher quality measure of epigenetic aging at the time of analysis becomes available, we we will substitute that instead. OSF preregistration link: https://osf.io/ahv2p/?view_only=

Domains (in gray) and sub-domains	Measure source	Psychometrics	Age preregistered Primary Outcome	Age preregistered Secondary Outcome	Measures and notes (All measures between grey lines measured in the same wave will be subject to multiple testing adjustments)
				6, 8	Expect slower DunedinPACE- pace of aging in high-cash group: Methylation pace of aging was developed from DNA-methylation analysis of Pace of Aging in the Dunedin Study birth cohort. Pace of Aging is a composite phenotype derived from analysis of longitudinal change in 18 biomarkers of organ-system integrity. Increments of methylation pace of aging correspond to “years” of physiological change occurring per 12-months of chronological time. We will also report GrimAge Acceleration, which we consider an exploratory analysis. GrimAge represents a DNA-methylation metric designed to predict morbidity and mortality. Briefly, the initial phase entailed the computation of models incorporating physiological indicators, age, sex, and smoking history, with the objective of optimizing mortality prediction within the Framingham Heart Study Offspring cohort. GrimAge will be based on principal components of DNA-methylation to bolster reliability and residualized for chronological age derived from sample receipt age to reflect accelerated biological age.

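### Two secondary child epigenetic outcomes can be replaced at the analysis stage, with no stated criterion, date, blinding or duty to report the registered score

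*SAP*

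**What the plan says.** The Phase 2 plan, under its additional details for age 6 and age 8 epigenetic processing and analysis, registers a directional hypothesis for child Epigenetic-g and then adds: "If a higher quality measure of epigenetic profile of cognitive functioning becomes available at the time of analysis, we will substitute that instead". Appendix Table 9 repeats the sentence in the Child DNA Methylation row, which lists ages 4, 6 and 8.

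In the Child Epigenetic Pace of Aging domain of the same table, the age-4 row says: "If a higher quality measure of epigenetic aging at the time of analysis becomes available, we we will substitute that instead".

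The remaining epigenetic outcomes carry no such sentence:
- Child pace of aging at ages 6 and 8 is tied to a named score: "We hypothesize slower pace of aging, as measured by DunedinPACE, in the high-cash gift group, relative to the low-cash gift group".
- Maternal pace of aging at ages 6 and 8 is tied to DunedinPACE in the same way.
- Maternal Epigenetic-g at age 4 (Appendix Table 10) has no substitution rule.

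At ages 6 and 8 GrimAge (children and mothers) and PhenoAge (mothers) are reported as exploratory analyses beside DunedinPACE.

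**The concern.** The wording is a rule, not an omission: the registered score is replaced, not supplemented, and the trigger is the time of analysis. By then the samples have been collected and assayed. Methylation scores are weighted sums over the same array data, so several can be computed at little cost before one is named as the outcome.

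A preregistered secondary test is useful because the reader knows that the outcome was not chosen in the light of the result. If a substitute score were reported as the registered outcome, with the named score missing, a reader could not easily tell a registered finding from a selected one. The waves are also linked: age-4 methylation was already being preprocessed when the Phase 2 plan was written, and ages 4, 6 and 8 are to be preprocessed again together. Age-4 group results could therefore inform the score used for the same children later.

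**Working it through.** **Does anything else in the documents close the gap?**

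| Possible safeguard | Where | Does it fix the score? |
|---|---|---|
| Site and sample exclusions come before scoring | SAP Phase 2, epigenetic section | No. It governs quality control, not which score is tested. |
| Preprocessing pipeline to be posted on OSF | Same section | No. It concerns preprocessing, and for ages 6 and 8 it is one "which will probably deviate from age 4 given new bioinformatic tools and lessons learned". |
| Multiple-testing adjustment within a domain and wave | SAP, Multiple comparisons; Appendix Table 9 | No. Each affected domain has one registered measure per wave, so an alternative that is tried and not reported is not counted. |
| Updates registered before each data collection wave | SAP Phase 2, Pre-registered Hypotheses | No. A swap at analysis comes after that point. |
| OSF link in the table rows | Appendix Table 9 | Unknown. The page could not be seen, and the substitution sentences do not refer to it for a selection rule. |

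**Inputs for the size.** The SAP's Phase 2 Statistical power section gives 800 children, split 40/60, with 80% power at p < .05. Directional hypotheses at ages 6 and 8 are tested one-tailed (Phase 2, Overview of Hypothesis Testing), which that section contrasts with prior preregistrations. The Phase 1 power statement is two-tailed, so age 4 is treated as two-tailed here. The correlation between a registered and a substitute score is not given. It is an assumption, shown as a range.

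**Check of the plan's own figure.** Detectable effect = (z_alpha + z_power) × sqrt(1/480 + 1/320), where the square root is 0.0722.
- One-tailed: (1.645 + 0.842) × 0.0722 = 0.179; the SAP states .18.
- Two-tailed: (1.960 + 0.842) × 0.0722 = 0.202; the SAP states .20.

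The nominal level and sidedness are therefore as the SAP states, and those figures are not in dispute.

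**Worst case: the more favourable score is kept.** With no true effect, let the test statistics of k scores be standard normal with common correlation r. The chance that at least one exceeds the critical value c is 1 − P(all k statistics < c). At r = 0 and k = 2 this is 1 − 0.95² = 0.0975 one-tailed, and 1 − 0.975² = 0.0494 in one direction of a two-tailed test. Other values come from the multivariate normal distribution.

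| Assumed r | Ages 6/8, two scores (nominal 5%) | Ages 6/8, three scores (nominal 5%) | Age 4, favoured direction, two scores (nominal 2.5%) |
|---|---|---|---|
| 0 | 9.8% | 14.3% | 4.9% |
| .5 | 8.8% | 11.8% | 4.5% |
| .7 | 8.0% | 10.3% | 4.2% |
| .9 | 6.8% | 8.0% | 3.5% |

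**Choice made without regard to group results.** One score is tested, and the error stays at its nominal 5%.

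**The case against.** The best defence is that the clause aims at better measurement. Epigenetic-g applies weights from adult blood to children's saliva, and the age-8 data come years after the plan was written, so a better score may well exist by then. The trigger is availability of a better measure, not a favourable result. The named score is public, so a swap would be visible, and the data are to be released about 18 months after each wave.

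Much of this stands. The intent is reasonable, and a substitute chosen on technical grounds alone does no harm to the error rate. But the documents do not secure that condition. Later data release lets others check a swap; it does not make the substitute a preregistered test.

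A reader might infer more than the text supports:
- *All epigenetic outcomes can be changed.* They cannot: child DunedinPACE at ages 6 and 8 and every maternal epigenetic outcome are free of the clause.
- *Primary conclusions are at risk.* Both affected outcomes are listed only as secondary.
- *The team plans to compute several scores with group labels to hand and keep the best.* No section says so, and nothing shows that selection has occurred.

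**Conclusion.** The point holds, within limits. For child Epigenetic-g at ages 4, 6 and 8 and child pace of aging at age 4, the plan permits the registered score to be replaced at analysis without any stated safeguard. That weakens the preregistration of these secondary tests; it does not remove the protection of preregistration from the trial.

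The error figures are upper bounds for result-driven choice between two scores. They run from about 6.8% to 9.8% against 5% at ages 6 and 8, and from about 3.5% to 4.9% against 2.5% in the favoured direction at age 4. They rest on assumed correlations of .9 to 0. The one-tailed figures should not be applied to pace of aging, which carries the clause only at age 4. The conclusion itself rests on the text and would stand without these numbers. The statement that no rule exists is limited to the supplied documents, since the OSF registration may contain one. This is a change that should be made, not one on which the trial's main results depend.

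**What to change.** Delete the substitution sentence in three places: the Phase 2 epigenetic section (child Epigenetic-g), the Child DNA Methylation row of Appendix Table 9, and the age-4 pace-of-aging row of the same table. Always test and report the named score as the registered outcome: Epigenetic-g at ages 4, 6 and 8, and DunedinPACE for child pace of aging at age 4. Report any newer score beside it, labelled exploratory, as the plan already does for GrimAge and PhenoAge. If age-4 scores have already been analysed, state which score was used and report the registered one.

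The change needs no new data and does not affect the planned sample size. Its one small cost is that a better score developed later would not be the confirmatory test. That can be met by re-registering the new score, with its version and a date, before any group comparison is made; the registered score should still be reported.
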